## Preliminary data

We performed immune phenotyping on peripheral blood samples collected from 12 subjects who underwent allogeneic HCT for chronic lymphocytic leukemia and who were treated with ibrutinib for post-transplant relapse. In these subjects, ibrutinib rapidly depleted pre-germinal-center B-cells ( $CD19^+CD38^+CD27^+IgD^+$ ), which have previously been associated with development of chronic GvHD. In contrast, memory B-cells ( $CD19^+CD27^+IgD^-CD38^-$ ) persisted, and total serum IgG levels were maintained despite ibrutinib treatment. Subset analysis of T-cells showed a 75% reduction in GATA3-expressing Th2 cells, while Tbet-expressing Th1 cells remained unaffected. T follicular cells ( $CD4^+CXCR5^+BCL6^+$ ) were likewise depleted rapidly from the circulation by ibrutinib treatment (Figure 1). Taken together, these preliminary results support the hypothesis that ibrutinib treatment after allogeneic HCT will result in Th1 polarization of the T-cell repertoire, preservation of  $CD8^+$  T-cells, and depletion of T follicular cells, all of which would be expected to reduce GvHD risk while maintaining beneficial anti-tumor alloreactivity. Of note, these preliminary data were obtained in subjects treated with ibrutinib for relapse, while the proposed study herein attempts to elucidate the role of maintenance ibrutinib on immune reconstitution and GvHD.

**Figure 1.** Changes in peripheral B-cell and T-cell subsets after treatment with ibrutinib in subjects with relapsed CLL after allogeneic HCT

## Correlative science aims

1. Perform immunophenotyping of peripheral-blood B- and T-cells before and after initiation of maintenance ibrutinib.
  - a. Evaluate Th1 polarization, effect on T follicular cells, and  $CD8^+$  cytotoxic T lymphocytes
  - b. Evaluate B-cell reconstitution by quantifying transitional, naïve, memory, and activated plasmablast fractions

- c. Determine concentrations of Th1 and Th2 cytokines in plasma
- 2. Characterize the B- and T-cell repertoire during and after ibrutinib maintenance using immune receptor high-throughput sequencing to assess clonal expansion of donor cytotoxic T-cells and follicular T-cells.
  - a. Compare to results from patients transplanted at our institution without maintenance ibrutinib
  - b. Quantify EBV-specific T-cell reconstitution
- 3. Assess B-cell function before and after initiation of maintenance ibrutinib
  - a. Evaluate for presence of alloreactive B-cells and H-Y antibodies in F->M allogeneic HCT
  - b. Quantify total serum immunoglobulin levels
  - c. Quantify protective anti-EBV and anti-tetanus antibodies
  - d. Assess levels of BAFF before, during, and after ibrutinib maintenance treatment

These laboratory studies will be correlated with clinical data (including onset, severity, and response of chronic GvHD and minimal residual disease detection of leukemia).

## 9. STUDY CALENDAR

Studies shown in *italics* are research studies, while evaluations shown in black represent clinical standard of care.

	Within 60 days of starting conditioning	Between Day +28 and Day +60	Start of ibrutinib (between Day +60 and Day +90)	Day +90	Day +180	9 months	1 year	15 months	18 months	2 years	Off Study
Eligibility determination	X	X									
History & physical	X	X	X	X	X	X	X	X	X	X	X
KPS assessment	X	X	X	X	X	X	X	X	X	X	X
Laboratory testing of hepatic and renal function	X	X	X	X	X	X	X	X	X	X	X
Transplant evaluation per institutional criteria	X										
Electrocardiogram (ECG)	X										
Hepatitis and HIV testing	X										
Pregnancy test (for women of childbearing potential)	X										
Bone marrow aspiration and/or biopsy with assessment of minimal residual disease	X	X		AML only*	AML only		AML only				
Minimal residual disease detection by peripheral-blood high-throughput sequencing (ClonoSEQ)	X	X		X*	X		X		X	X	
Assessment of concomitant medications	X	X	X	X	X	X	X	X	X		X
Acute GvHD assessment		X		X							
Chronic GvHD assessment				X	X	X	X	X	X	X	X
Ibrutinib (study drug)						X -----			X		
Adverse event evaluation						X-----				X	
Blood draw for biological studies	X		X	X	X		X		X	X	
Blood sample from HCT donor (related only)	X										

For the Day +90 and Day +180 timepoints, the relevant evaluations may be performed within +/- 2 weeks of the specified timepoint. For the 9-month, 1-year, 15-month, and 18-month timepoints, the relevant evaluations should be performed within +/- 4 weeks of the specified timepoint.

\* Please note: Okay to omit Day +90 MRD testing and Day +90 biopsy if previous biopsy (between Day +28 and Day +60) showed no evidence of disease.

## **10. MEASUREMENTS**

### **10.1 Primary and Secondary Outcome measures**

The primary outcome measure is the incidence of relapsed leukemia at 18 months after allogeneic HCT. This is an efficacy endpoint.

Secondary endpoints include the incidence of acute GvHD Grades II–IV and III–IV at Day +180 after allogeneic HCT, the incidence of chronic GvHD at 18 months after allogeneic HCT, and the incidence of detectable minimal residual disease at 1 year after allogeneic HCT.

#### **10.1.1 Relevant Subsets**

The primary and secondary outcomes will be measured on all enrolled subjects.

#### **10.1.2 Measurement Definition**

For the primary outcome measure, relapsed leukemia is defined as > 5% leukemic blasts detected in bone marrow or peripheral blood. Subjects will also be considered to have relapsed leukemia if they receive any active treatment for progressive leukemia after allogeneic HCT, even if they have <5% leukemic blasts. Withdrawal of immunosuppression alone is not considered an active treatment for progressive disease.

For the secondary outcome measures, acute GvHD will be graded and scored according to standard criteria (Appendix C). Chronic GvHD will be graded and scored according to the 2014 NIH consensus criteria (Appendix D). Minimal residual disease will be assessed by high-throughput sequencing (ClonoSEQ) for subjects with ALL, and by high-sensitivity flow cytometry for subjects with AML or acute biphenotypic leukemia. Minimal residual disease will be considered present if  $> 1 \times 10^{-6}$  leukemic clones are detected by ClonoSEQ (20), or if any aberrant blasts matching the original leukemic immunophenotype are detected by high-sensitivity flow cytometry (21).

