### **3.2 Exclusion Criteria**

#### **3.2.1 Exclusion Criteria for enrollment (pre-transplant)**

- Active involvement of the central nervous system with malignancy (previous CNS involvement is allowed if clearance of CNS disease has been documented prior to enrollment)
- Pregnant or breastfeeding
- Karnofsky Performance Status < 60%
- Active leukemia (> 5% leukemic blasts in peripheral blood or bone marrow)
- Non-hematologic malignancy with a life expectancy of < 5 years
- Known history of human immunodeficiency virus (HIV) or active hepatitis C virus (HCV) or hepatitis B virus (HBV) infection. *Subjects who are positive for hepatitis B core antibody or hepatitis B surface antigen must have a negative polymerase chain reaction (PCR) result before enrollment. Those who are PCR-positive will be excluded.*
- Known bleeding disorders (eg, von Willebrand's disease) or hemophilia.
- History of other malignancies, except:
  - Malignancy treated with curative intent and with no known active disease present for  $\geq$  3 years before the first dose of study drug and felt to be at low risk for recurrence by treating physician.
  - Adequately treated non-melanoma skin cancer or lentigo maligna without evidence of disease.
  - Adequately treated carcinoma *in situ* without evidence of disease.

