#### **3.2.2 Exclusion Criteria (prior to ibrutinib administration)**

- Active and uncontrolled acute GvHD Grades III or IV
- Use of secondary therapy for acute GvHD at any time (defined as any systemic therapy intended to treat acute GvHD besides corticosteroids)
- Requirement for anticoagulation with warfarin or other Vitamin K antagonists (concomitant use of other anticoagulants is permitted)
- Relapsed leukemia (> 5% leukemic blasts in peripheral blood or bone marrow after allogeneic HCT)
- Karnofsky Performance Status < 60%
- Chemotherapy  $\leq$  21 days prior to first administration of study treatment and/or monoclonal antibody  $\leq$  6 weeks prior to first administration of study treatment
- Vaccinated with live, attenuated vaccines within 4 weeks of first dose of study drug.
- Currently active, clinically significant cardiovascular disease, such as uncontrolled arrhythmia or Class 3 or 4 congestive heart failure as defined by the New York Heart Association Functional Classification; or a history of myocardial infarction, unstable angina, or acute coronary syndrome within 6 months prior to randomization.

- History of stroke or intracranial hemorrhage within 6 months prior to screening
- Any life-threatening illness, medical condition, or organ system dysfunction that, in the investigator's opinion, could compromise the subject's safety or put the study outcomes at undue risk.
- Major surgery within 4 weeks of first dose of study drug.
- Any uncontrolled active systemic infection.
- Unresolved toxicities from prior anti-cancer therapy, defined as having not resolved to Common Terminology Criteria for Adverse Event (CTCAE, version 4), Grade ≤ 1, or to the levels dictated in the inclusion/exclusion criteria with the exception of alopecia
- Unable to swallow capsules or malabsorption syndrome, disease significantly affecting gastrointestinal function, or resection of the stomach or small bowel, symptomatic inflammatory bowel disease or ulcerative colitis, or partial or complete bowel obstruction
- Requires treatment with a strong cytochrome P450 (CYP) 3A4/5 inhibitor (see Appendix E).
- Unwilling or unable to participate in all required study evaluations and procedures.
- Unable to understand the purpose and risks of the study and to provide a signed and dated informed consent form (ICF) and authorization to use protected health information (in accordance with national and local subject privacy regulations).

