### **Prohibited Concomitant Medications**

Any chemotherapy, anticancer immunotherapy, experimental therapy, or radiotherapy is prohibited while the subject is receiving study treatment with ibrutinib. Localized, hormonal, or bone-sparing treatment for non-hematologic may be considered with approval of the PI.

The Sponsor-investigator must be notified in advance (or as soon as possible thereafter) of any instances in which prohibited therapies are administered.

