2. Use of secondary therapy for acute GvHD at any time (defined as any systemic therapy intended to treat acute GvHD besides corticosteroids)			
3. Requirement for anticoagulation with warfarin or other Vitamin K antagonists (concomitant use of other anticoagulants is permitted)			
4. Relapsed leukemia (> 5% leukemic blasts in peripheral blood or bone marrow at any point after allogeneic HCT)			
5. Karnofsky Performance Status <60%			
6. Chemotherapy ≤ 21 days prior to first study drug dose and/or monoclonal antibody ≤ 6 weeks prior to first study drug dose			
7. Vaccinated with live, attenuated vaccine within 4 weeks of first study drug dose			
8. Currently active, clinically significant cardiovascular disease (eg, NYHA Class III or IV heart failure, uncontrolled arrhythmia, or acute coronary syndrome within 6 months of first study drug dose)			
9. History of stroke or intracranial hemorrhage within 6 months of first study drug dose			
10. Any life-threatening illness, medical condition, or organ dysfunction that, in the investigator's judgement, could compromise the subject's safety or put the study outcomes at undue risk.			
11. Major surgery within 4 weeks of first study drug dose			
12. Active, uncontrolled systemic infection			

Withdrawal Criteria (From IRB-approved protocol)	Yes	No	Supporting Documentation*
13. Unresolved toxicities from prior anti-cancer therapy (not resolved to CTCAE v4 Grade 1 or less, or to the levels described in these criteria, except alopecia)			
14. Unable to swallow capsules or malabsorption syndrome, disease significantly affecting gastrointestinal function, or resection of the stomach or small bowel, symptomatic inflammatory bowel disease or ulcerative colitis, or partial or complete bowel obstruction			

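### The relapse definition leaves out untreated extramedullary relapse with marrow and blood blasts at or below 5%, and the pre-ibrutinib relapse exclusion uses only the blast part of that definition

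*Combined protocol and SAP*

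**What the plan says.** Section 10.1.2 gives two routes to the primary event. The first is a blast count: "relapsed leukemia is defined as > 5% leukemic blasts detected in bone marrow or peripheral blood". The second is treatment: "Subjects will also be considered to have relapsed leukemia if they receive any active treatment for progressive leukemia after allogeneic HCT", which applies even when blasts are low. It then narrows the second route: "Withdrawal of immunosuppression alone is not considered an active treatment for progressive disease". Neither route names CNS or other extramedullary disease. Section 10.1.3 makes bone marrow examination the definitive assessment when monitoring raises concern.

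Active CNS disease is an exclusion only at pre-transplant enrollment (3.2.1), where "previous CNS involvement is allowed if clearance of CNS disease has been documented prior to enrollment". It is not repeated among the criteria applied before ibrutinib.

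The relapse exclusion before ibrutinib in 3.2.2 reads "Relapsed leukemia (> 5% leukemic blasts in peripheral blood or bone marrow after allogeneic HCT", and item 4 of the withdrawal criteria in Appendix B reads "Relapsed leukemia (> 5% leukemic blasts in peripheral blood or bone marrow at any point after allogeneic HCT". Both use the blast route only. Section 4.2 stops ibrutinib at leukemia relapse without defining the term, and follows all enrolled subjects for relapse and survival to 18 months after transplant.

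Section 12.1 tests the 18-month relapse rate against a fixed historical 45%, with 50 enrolled subjects, two-sided 0.05 and 84% power if the true rate is 25%. Section 12.3 makes the primary analysis intention-to-treat and plans a subset analysis of subjects who receive at least one dose.

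**The concern.** The trial enrolls ALL and AML and admits subjects with cleared CNS disease, so relapse outside marrow and blood is possible. If such a relapse is documented but the subject is managed palliatively, dies before therapy, or only has immunosuppression withdrawn, neither route in 10.1.2 is met and the subject is scored as free of relapse. Taken alone, this gap can only lower the counted rate, and a single-arm trial has no control group that would under-count in the same way.

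The dosing criterion raises a second, separate issue. The protocol uses one definition of relapse to score the endpoint and a narrower one to decide who may start a drug meant to prevent relapse. A subject treated for progression at 5% blasts or fewer before dosing already has a primary event, yet is not excluded as relapsed. The same holds for a subject with extramedullary relapse, treated or not. Such a subject, if dosed, enters the treated subset of 12.3 either already carrying an event or with a relapse that is not counted.

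**Working it through.** **1. What 10.1.2 counts**

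| Course after transplant, to 18 months | Blast route | Treatment route | Scored |
|---|---|---|---|
| Extramedullary relapse, actively treated | not needed | met | event |
| Extramedullary relapse, untreated, later >5% marrow or blood blasts | met | not met | event |
| Extramedullary relapse, immunosuppression withdrawn only, blasts never >5% | not met | not met | no event |
| Extramedullary relapse, no treatment, blasts never >5% | not met | not met | no event |

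Only the last two rows are misclassified.

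**2. The plan's own power**

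Inputs from 12.1: n = 50, null rate 0.45, alternative 0.25, two-sided 0.05. The protocol names no test. I assume an exact binomial test with 0.025 in the lower tail:

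P(X ≤ c) = Σ (k = 0 to c) C(50, k) p^k (1 − p)^(50 − k)

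- At p = 0.45: P(X ≤ 15) = 0.0220 and P(X ≤ 16) = 0.0427, so success requires 15 or fewer relapses.
- At p = 0.25: P(X ≤ 15) = 0.837, which matches the stated 84%.
- For the 45 treated subjects, success at 13 or fewer gives 0.784, which matches the stated 78%.

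**3. What one uncounted relapse does**

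| Relapses counted of 50 | Lower-tail p against 45% | 95% exact upper limit | Two-sided exact p (minimum likelihood) |
|---|---|---|---|
| 15 (30%) | 0.022 | 44.6% | 0.034 |
| 16 (32%) | 0.043 | 46.7% | 0.066 |

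The conclusion changes only if the true count is exactly 16 and one of those relapses is uncounted. P(X = 16) = 0.0427 − 0.0220 = 0.021 at a 45% rate, and 0.065 at 25%. These are upper bounds for the one-case scenario. They must be multiplied by the chance that one of the 16 is uncounted, and the documents give no figure for that.

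As illustration only, suppose a share m of all subjects has an uncounted relapse and the true total rate is 45%, so the counted rate is 0.45 − m. The chance of success is then 2.20% at m = 0, 2.27% at 0.1%, 2.35% at 0.2%, 3.0% at 1% and 4.2% at 2%. Nothing in the documents supports any particular m.

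**4. Whether other criteria stop a relapsed subject before ibrutinib**

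The first dose may be given up to Day +90.

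- Chemotherapy washout (3.2.2: "21 days prior to first administration of study treatment and/or monoclonal antibody"): excluded at 21 days or fewer, so the latest passing day is 90 − 22 = Day +68.
- Antibody washout of 6 weeks (42 days): the latest passing day is 90 − 43 = Day +47.
- Radiotherapy: section 4.1 says "radiotherapy is prohibited while the subject is receiving study treatment with ibrutinib". No washout before ibrutinib is given.
- Haematologic criteria in 3.1.2 (ANC >0.75 × 10⁹/L, platelets >50 × 10⁹/L, hemoglobin >8.0 g/dL, unsupported for at least 7 days) and toxicity resolved to Grade 1 or less: these stop many recently treated subjects, but a subject who has recovered passes.
- Investigator judgement on life-threatening illness or risk to study outcomes: this could reasonably be used for known relapse, but it is discretionary.
- The coordinating center reviews the checklist before dosing, but Appendix B item 4 carries the same blast-only wording.

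No criterion before dosing excludes relapse as 10.1.2 defines it.

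**The case against.** A reader might infer that CNS and extramedullary relapse is not counted at all. The text does not support that: the treatment route has no restriction by site, and treatment or blasts above 5% at any later time to 18 months turns the case into an event. What remains needs documented extramedullary disease, no active treatment, and blasts never above 5%. The documents do not show that any subject would meet all three conditions.

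A reader might also infer that the type I error is inflated in the drug's favour. That is not supported either. There is no rate for such cases, and the documents do not say how the studies behind the 45% defined relapse. The treatment route also counts subjects below the blast threshold, which would raise the count against a purely blast-based historical figure. The net direction is unknown.

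On dosing, it would be too strong to say that relapsed subjects can freely start ibrutinib. The washouts, haematologic recovery, toxicity rule and investigator judgement will stop many of them, and 4.2 stops the drug for relapse with no blast qualifier. Relapse is also listed in section 7.2 among the events to be recorded, so the information need not be lost.

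Lastly, leaving out withdrawal of immunosuppression as active treatment is a deliberate and defensible choice. It does not follow that the documented relapse itself should go uncounted. All of this limits the size of the point. It leaves the misclassification in 10.1.2 and the mismatch between the endpoint and the dosing criterion in place.

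**Conclusion.** The point holds as a minor one. The rule in 10.1.2 is complete for treated relapse but scores a narrow group of documented extramedullary relapses as no event. The group is probably very small and cannot be sized from the documents. One such case matters only at a true count of 16 of 50, assuming the exact binomial test that reproduces the stated power. Whether it favours the drug against 45% depends on whether the historical figure included these relapses.

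The mismatch in the pre-ibrutinib exclusion is an internal inconsistency that needs no assumption about frequency. It does not change the intention-to-treat primary result, because all enrolled subjects are analysed whether dosed or not. It affects who is dosed and the composition of the treated subset in 12.3.

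**What to change.** - In 10.1.2, add a third route: extramedullary (including CNS) leukemia confirmed by CSF cytology or flow cytometry, tissue biopsy, or imaging judged diagnostic by the treating physician in routine care, at any blast percentage, dated at first documentation. State that no added surveillance is required.
- In 3.2.2, Appendix B item 4 and 4.2, refer to the 10.1.2 definition in place of a partial restatement or an undefined term.
- Record the site of relapse, and report a count using only the blast and treatment routes as a sensitivity analysis.

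The cost is wording in four places, one case report form field and one extra tabulation; no new procedure is needed. The downside is that the observed relapse rate may be slightly less favourable, and the comparison slightly stricter than history if the 45% left out extramedullary relapse. The sensitivity count would show how much this matters.

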#### **10.1.3 Measurement Methods and Time Points**

The primary outcome will be measured by bone marrow examination at Day +90; Day +180; and 1 year after allogeneic HCT in subjects with AML or myeloid leukemias, and by peripheral-blood high-throughput sequencing on Day +90; Day +180; 1 year; 18 months; and 2 years post-transplant in subjects with ALL. Minimal residual disease detection by high-throughput sequencing is not itself diagnostic of relapse, but should prompt a bone marrow examination to assess definitively for relapse. Routine monitoring of peripheral blood counts and differential will also be performed according to clinical standards of care, with bone marrow examination performed in response to any concerning findings to assess for relapse.

The secondary outcomes will be measured as follows: acute GvHD will be scored weekly (if returning to the transplant center that frequently) from initiation of ibrutinib through Day +100 using the criteria described above. Chronic GvHD will be assessed at Day +180, at 9 months, at 1 year, at 15 months, and at 18 months after allogeneic

HCT, using the criteria described above. Minimal residual disease will be assessed as described above on Day +90; Day +180; 1 year; and 18 months after allogeneic HCT.

For the Day +100 and Day +180 timepoints, the relevant evaluations may be performed within +/- 2 weeks of the specified timepoint. For the 9-month; 1-year; 15-month; and 18-month timepoints, the relevant evaluations should be performed within +/- 4 weeks of the specified timepoint.

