**Start of preparative regimen through Day +60 to Day +90:**

- Pre-conditioning blood sample from HCT recipient for high-throughput sequencing, flow cytometry, and CyTOF (**research**)
- Blood sample from HCT donor (related only), as a baseline to investigate development of post-transplant GVL effects (**research**)
- Disease reassessment between Day +28 and Day +60, including bone marrow examination and assessment of minimal residual disease as described above (**standard of care**)

**Prior to administration of ibrutinib (Day +60 to Day +90; all studies should be done within 2 weeks of starting ibrutinib):**

- Laboratory assessment of hepatic and renal function (**standard of care**)
- Assessment of acute GvHD presence, severity, and therapy history (**standard of care**)

- History and physical, including Karnofsky Performance Status (**standard of care**)
- Assessment of concomitant medications (**standard of care**)
- Collection of peripheral blood samples for mixed lymphocyte reactions, Th1/Th2 assays, and other correlative science endpoints (**research**)

Ibrutinib will be initiated between Day +60 and Day +90, after confirmation that the subject meets all relevant eligibility criteria. The drug will be dosed, and doses modified, as described below. The following assessments will be performed after initiation of ibrutinib:

**After start of ibrutinib until 2 years post-transplant** (tests should be performed +/- 2 weeks of given time points through Day +180, and +/- 4 weeks of given timepoints after Day +180):

- History, physical examination, and laboratory assessment of hematologic and chemistry tests per institutional standard practice (**standard of care**)
- Acute GvHD assessment weekly through Day +100 (**standard of care**)
- Chronic GvHD assessment at 6 months, 9 months, 12 months, 15 months, 18 months, and 2 years post-transplant (**standard of care**)
- Toxicity assessment at baseline (before starting ibrutinib), weekly through Day +100, monthly until Day +180, and then at 9 months, 12 months, 15 months, and 18 months post-transplant (**research**), unless ibrutinib has been permanently discontinued

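### Acute GvHD incidence is an endpoint at Day +180, but scheduled acute GvHD scoring stops at Day +100, leaving the last 80 of 180 days without a scheduled grade

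*Combined protocol and SAP*

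**What the plan says.** Section 10.1 lists among the secondary endpoints "the incidence of acute GvHD Grades II–IV and III–IV at Day +180 after allogeneic HCT". Section 10.1.1 sets the population: "The primary and secondary outcomes will be measured on all enrolled subjects". Section 10.1.2 says that acute GvHD is graded by the criteria in Appendix C.

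The schedule appears in three places:

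- **Section 10.1.3:** "acute GvHD will be scored weekly (if returning to the transplant center that frequently) from initiation of ibrutinib through Day +100". The window is stated as: "For the Day +100 and Day +180 timepoints, the relevant evaluations may be performed within +/- 2 weeks of the specified timepoint".
- **Section 4:** before the first dose, "Assessment of acute GvHD presence, severity, and therapy history"; after it, "Acute GvHD assessment weekly through Day +100".
- **Section 9 (calendar):** as the table reads in the available text, acute GvHD is marked at the Day +28 to +60 visit and at Day +90, and nowhere later.

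The GvHD assessment that is scheduled at Day +180 is the chronic one: "Chronic GvHD will be assessed at Day +180" (Section 10.1.3), using Appendix D.

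**The concern.** An incidence at Day +180 needs every subject's acute GvHD status and highest grade up to that day. All three statements of the schedule end before it. Someone following the protocol exactly would reach Day +180 with no required Appendix C grade since about Day +100.

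A second mismatch lies in the population. The endpoint covers everyone enrolled, but weekly scoring begins with ibrutinib. Subjects who never start the drug have no weekly series, only the pre-ibrutinib assessment and the calendar marks.

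Section 7.2 says GvHD incidence will be reported with the secondary outcomes. If ungraded time is read as free of acute GvHD, the reported incidence can only be too low. Section 8 expects ibrutinib to reduce GvHD risk, so the error would run in the direction the investigators hope to see.

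**Working it through.** The plan gives no figure of its own for this gap, so there is none to reproduce. The check compares the endpoint's date with the schedule and then asks whether another scheduled assessment fills the difference.

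**Inputs**

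- Endpoint day: 180 (Section 10.1)
- Last scheduled acute scoring: Day 100 (Sections 4 and 10.1.3)
- Visit window: 14 days either side (Section 10.1.3)
- Last acute GvHD calendar mark: Day 90 (Section 9)
- Ibrutinib start: Day 60 to Day 90 (Section 4)
- Enrolled 50, of whom 45 are assumed treated (Section 12.1)

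**Length of the final gap** (endpoint day minus last scheduled acute grade)

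| Last acute grade | Gap, days | Share of 180 days |
|---|---|---|
| Day +100 as written | 180 − 100 = 80 | 80/180 = 44% |
| Day +114 (100 + 14, end of window) | 180 − 114 = 66 | 66/180 = 37% |
| Day +90 (calendar mark) | 180 − 90 = 90 | 90/180 = 50% |

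These are calendar days, not expected events.

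**Coverage after the first dose**

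- Start at Day +60: 180 − 60 = 120 days to the endpoint, of which 100 − 60 = 40 are scored and 80 are not (80/120 = 67%).
- Start at Day +90: 180 − 90 = 90 days, of which 100 − 90 = 10 are scored and 80 are not (80/90 = 89%).

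**Weight of one missed case**

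- All enrolled: 1/50 = 2.0 percentage points.
- Treated subset: 1/45 = 2.2 percentage points.
- Never treated, on the plan's assumption: 50 − 45 = 5 subjects without weekly scoring.

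**Other routes between Day +100 and Day +180**

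- *Chronic GvHD assessment at Day +180.* Appendix D lists features shared by acute and chronic GvHD, but its organ scoring is done only once chronic GvHD is diagnosed, and it yields no Appendix C grade.
- *Monthly toxicity assessment to Day +180 (Section 4).* It stops if ibrutinib is permanently discontinued. Section 7.2 grades adverse events by CTCAE and also mentions a three-point scale; neither is Appendix C.
- *Recording of GvHD events (Section 7.2).* GvHD is to be recorded, with no acute grade or date of grading specified. One of the section's definitions of an adverse event begins with receipt of study drug.
- *History and physical examination at Day +180 (Section 9).* No acute GvHD grading is attached to it.

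Each route could bring a late case to notice. None schedules the grade that the endpoint requires.

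**Who could be miscounted.** Subjects already graded III–IV by Day +100, including those kept off ibrutinib for uncontrolled Grade III–IV disease, are events under both definitions and are not lost. A subject graded II by Day +100 already counts for II–IV but could be missed for III–IV on later worsening. A subject with no acute GvHD, or Grade I only, by Day +100 could be missed for both.

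**The case against.** The mismatch in dates is hard to dispute; the argument is over how much it matters.

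- **The 44% may not measure lost information.** The calendar has no acute GvHD mark before Day +28 either, and nobody treats that as lost time, because a later visit can pick up earlier onset. This is fair as a warning against reading 44% as a share of cases. But the early interval is followed by scheduled acute assessments, and the interval after Day +100 is not.
- **The 90-day upper figure rests on a calendar row that is itself incomplete.** The row omits the pre-ibrutinib assessment that Section 4 requires. That stands: 80 days is the main figure and 90 is only the widest reading.
- **Late cases would probably reach the record.** Besides the routes above, Section 11.4 allows upload from the transplant database and lists GvHD history and assessment among the information that may be collected, and Section 7.2 has GvHD incidence reported to the IRB each year. These make complete loss unlikely, but do not secure a uniform Appendix C grade and onset date in every subject.
- **The bias is conditional.** Nothing in the plan says that ungraded time counts as event-free, and no estimator is given for this endpoint. That also stands: the direction is known only under that reading, and the 2.0 points per case assumes a simple proportion of 50.

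**Conclusion.** The concern holds. The endpoint is set at Day +180, and scheduled acute GvHD scoring ends 80 days earlier (66 to 90 days by the readings above). The unscored part is two thirds or more of the time from first dose to the endpoint. The number of cases that would be missed cannot be derived, because the documents give no rate of acute GvHD after Day +100. A downward bias assumes that ungraded time is read as event-free.

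The consequence is limited to one secondary endpoint, for which no target, power or decision rule is stated. The primary relapse endpoint, its power and the non-relapse mortality stopping rule do not depend on it. It should be corrected because the plan as written does not schedule the measurement it promises to report, and the correction is cheap.

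**What to change.** Reconcile Sections 4, 9, 10.1 and 10.1.3 in one of two ways.

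- **(a) Keep Day +180.** Add an acute GvHD mark at the existing Day +180 visit. For every enrolled subject, whether or not ibrutinib was started or continued, record the maximum Appendix C grade since transplant and the onset date, so that both II–IV and III–IV can be derived. Use chart review where there is no visit. Cost: one calendar mark, a few case report form fields, and some chart review for subjects never treated or off drug.
- **(b) Move the endpoint to Day +100.** Define it as the maximum Appendix C grade from transplant to Day +100 in all enrolled subjects. Cost: little new data, though never-treated subjects still need chart review because they have no weekly scoring. It gives up the 80 days to Day +180, most of the period after the first dose that the endpoint was meant to cover.

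Option (a) preserves the stated endpoint for little more effort. Under either option, report how many subjects lack acute grading to the chosen day, and do not count them as event-free by default.
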